7.1.2 Key Secondary Outcomes (Primary Objective)

7.1.2.1 NOWS Severity

NOWS severity will be assessed by total days of opioid treatment during the hospital stay, which is a definition that has been used in past research.⁶⁰ This outcome will be abstracted from the medical record.

7.1.2.2 *Postpartum Illicit Opioid Abstinence*

Illicit opioid abstinence postpartum will be assessed in a similar fashion to illicit opioid abstinence during pregnancy (see **section 7.1.1**).

7.2 **Secondary Outcome Measures (Primary Objective)**

7.2.1 **Mother Secondary Outcomes**

7.2.1.1 *BUP Medication Adherence*

Adherence to BUP treatment during pregnancy through 12 months postpartum is a clinically important outcome due to the heightened vulnerability to relapse¹³ and overdose²² during this period. Adherence to BUP treatment during pregnancy will be scored as the number of days of adherence divided by the number of days between randomization and delivery. Postpartum adherence to BUP treatment will be scored as the number of days of adherence post-hospital-discharge divided by the number of post-hospital-discharge days in the 12-month postpartum phase. Adherence to BUP-XR will be based on study records (i.e., BUP-XR Injection documentation). For BUP-XR, the receipt of a weekly injection will be scored as 7 days of adherence. If a particular day is covered by two injection windows (e.g., injections on study day 7 and study day 13, where study day 6 overlaps the two seven-day windows), the adherent day will only be counted once. For monthly injections, a participant will be considered as adherent for 28 days and overlapping intervals are handled similarly as for the weekly injections. Adherence to BUP-SL will be defined as: 1) study records showing that BUP-SL was dispensed to the participant (i.e., BUP-SL Dispensing documentation); 2) self-reported adherence will be assessed at the weekly Medication Check Visits; and 3) UDSs positive for buprenorphine/norbuprenorphine. In cases where participants discontinue study medication to transfer to an alternative treatment (e.g., methadone, extended-release naltrexone), a score of 0 days of adherence will be given for the time period post discontinuation. The rationale for not “crediting” receipt of methadone or extended-release naltrexone as adherence is that a switch to an alternative medication is an indicator that BUP-XR / BUP-SL was, in some way, ineffective for the participant and the score of 0 is consistent with the lack of effectiveness. In cases where participants discontinue study medication to transfer to BUP from an alternative provider or were provided non-study BUP during hospital stays or incarceration, a release of information will be obtained, and adherence will be based on clinic/pharmacy records (BUP-XR) or, for BUP-SL, on clinic/pharmacy records along with participant self-report and study UDSs if available. For the case where clinic/pharmacy records could not be obtained for any reason, the participant will be considered non-adherent. If participants drop out of the study prematurely, they will be considered non-adherent for all days after drop-out. In the case of intermittent missing UDSs (e.g., UDSs not collected for any reason but the participant did not drop out), then adherence will be based on study/clinic/pharmacy records and self-report.

7.2.1.2 *Drug and Alcohol Abstinence*

Drug and alcohol abstinence during pregnancy and postpartum are secondary outcomes and will be assessed in a fashion similar to the assessment of illicit opioid abstinence, but rather than being restricted to illicit opioid use, will include alcohol and other drugs of abuse. Missing urine samples will be imputed as positive.

7.2.1.3 *The Opioid Craving Scale*

Craving will be assessed with the Opioid Craving Scale, which was utilized in CTN-0030 and shown to have predictive validity.¹¹² The total score is calculated by averaging the scores from three visual analogue scales which assess craving, cue-induced craving, and likelihood of using.

7.2.1.4 *Adequacy of Prenatal Care Utilization*

Kotelchuck's Adequacy of Prenatal Care Utilization (APNCU) index,¹¹³ which is a well-established index,¹¹⁴ will be used to assess the adequacy of prenatal care. The APNCU includes two indices that are combined to obtain a total score. One index is the timing of prenatal care initiation scored in 4 categories [EGA months: 1) 1 and 2; 2) 3 and 4; 3) 5 and 6; and 4) 7 to 9]. The second is the ratio of observed to expected visits based on the length of time between the first prenatal care visit and delivery, scored in 4 categories: 1) Inadequate (received less than 50% of expected visits); 2) Intermediate (50%-79%); 3) Adequate (80%-109%); 4) Adequate Plus (110% or more). The information for the APNCU will be derived from either medical records or the birth certificate. The % of expected visits attended prior to study randomization will be included as a baseline covariate in analyses.

7.2.1.5 *The Short Opiate Withdrawal Scale (SOWS)-Gossop*

The SOWS-Gossop¹¹⁵ will be used to measure opioid withdrawal symptoms. The SOWS-Gossop, which is a self-administered scale that includes 10 items, rated on a scale of 0 (none) to 3 (severe), is a validated instrument with good reliability.¹¹⁶ It will be completed following the schedule in **Table 3**.

7.2.2 Infant Secondary Outcomes

7.2.2.1 *Other NOWS-related Outcomes*

Five additional NOWS-related outcomes will be abstracted from the medical record:

1. use of opioid medication for NOWS symptoms (yes/no); if yes, medication used;
2. infant hospital LOS defined as the infant's age, in days, at discharge;
3. use of adjunct medications (e.g., phenobarbital, clonidine);
4. NOWS scoring assessment used and peak score; and
5. an ICD-10 code indicative of NOWS (Yes/No); infants will be scored as "yes" if their medical record includes an ICD-10 code of P96.1 (neonatal withdrawal symptoms from maternal use of drugs of addiction) and/or P96.2 (withdrawal symptoms from therapeutic use of drugs in newborn) within the first 10 days of life.

7.2.2.2 *Discharge Outcomes*

Discharge outcomes to be abstracted from the medical record include: custody (e.g., mother, other relative, foster/adoptive family), medications at discharge (e.g., phenobarbital, clonidine), and an open case with child protective services (yes/no).

7.2.2.3 *Infant Development*

The 6- and 12-month versions of the Ages and Stages Questionnaire, third edition (ASQ-3)⁷¹ will be used to screen for developmental issues in the infants. The ASQ-3 is a validated, parent-administered screen used throughout the world⁷¹⁻⁷³ and deemed appropriate for assessing infants

exposed to opioids in utero.¹³ The outcome of interest is whether or not the infant scores below the ASQ-3 cut-off (yes/no). The ASQ-3 will be completed by the infant's caregiver, which may or may not be the birth mother. Thus, flexibility in the collection of this assessment will be allowed, including collection via mail. Infant development can be significantly impacted by psychosocial stressors and, thus, the individual completing the ASQ-3 will also be asked to complete The Family Psychosocial Screener (see **section 7.6.3**). Caregivers of infants scoring below the cut-off will be offered a referral for further evaluation.

7.3 Safety Measures of the Primary Objective

7.3.1 Adverse Events (AEs)

AEs will be assessed by study staff as outlined in **Table 3**. If an AE requires medical attention, it should be reported to a site MC immediately. For visits held via telemedicine or at an external location, research staff will contact a qualified medical clinician via phone to coordinate an assessment via telemedicine as quickly as possible; ideally this assessment will occur while the staff and participant are together at the external location. Recording of safety information, including Adverse Events, is described in **section 11.17**.

7.3.2 The Hospital Anxiety and Depression Scale (HADS)

The Hospital Anxiety and Depression Scale (HADS)¹¹⁷ will be used to assess for symptoms of depression and anxiety. The HADS is a brief, validated instrument that screens for both depression and anxiety¹¹⁸ and will be completed following the schedule outlined in **Table 3**. Participants who score in the range for possible depression (total depression score of 8 or higher) or anxiety (total anxiety score of 8 or higher) should be assessed by a qualified clinician before leaving the clinic as specified in the site clinical standard operating procedure (SOP). For visits held via telemedicine or at an external location, research staff will contact a qualified clinician via phone to coordinate an assessment via telemedicine as quickly as possible; ideally this assessment will occur while the staff and participant are together at the external location. If a participant is assessed and, at subsequent visits, continues to have the same elevated score, then the need for reassessment is at the discretion of a qualified clinician; a subsequent increase in the HADS score would require assessment by a qualified clinician.

7.3.3 Prior/Concomitant Medications

All medications taken by the participant since the start of her pregnancy and during the active study will be documented on a Prior/Concomitant Medications assessment (see **Table 3**). All medications taken by the participant while in the study should ideally be pre-approved by the MC whenever possible to avoid interactions with the study drugs.

7.3.4 Fetal Outcomes

Adverse fetal outcomes, including gestational age at time of outcome, will be abstracted from the medical record. These outcomes include: spontaneous abortions/miscarriages, stillbirth (i.e., death of a fetus at any time after the 20th week of pregnancy), pregnancy terminations and indications for termination (elective or medical and, if medical, the reason for termination).

7.3.5 Maternal Delivery Outcomes

Maternal delivery outcomes to be abstracted from the medical record include: cesarean section, abnormal fetal presentation during delivery, medical complications at delivery, and analgesic receipt during labor and delivery, postpartum, and upon discharge.

7.3.6 Birth/Neonatal Outcomes

Birth/neonatal outcomes will be abstracted from the medical record. These outcomes include: head circumference, weight and length at birth, gestational age at delivery, and 1-minute and 5-minute Apgar (activity, pulse, grimace, appearance, respiration) scores. Other outcomes will include: major birth defects, neonatal death, and need for resuscitation. Adverse birth outcomes will be characterized, including (if preterm), the reason for preterm birth (e.g., fetal distress, etc.). Other adverse neonatal outcomes will be captured including respiratory distress symptoms, need for respiratory support in the neonatal unit, feeding problems (need for nasogastric tube), seizures, and other co-morbidities.

7.3.7 Injection Site Examination

Participants will be asked to immediately report any injection site reactions to study staff for evaluation, monitoring, and possible referral, as needed. For weekly injections, the site of the last BUP-XR injection will be examined at the weekly Medication Check Visits. For monthly injections, the BUP-XR injection site will be examined at the weekly Medication Check Visit following the visit during which the injection was given. Injection site reactions will be documented on the Injection Site Reaction Reporting form.

7.3.8 Opioid Overdose Tracking

Some evidence suggests that women with OUD are at heightened risk for overdose during the postpartum period.²² During the study, the participant will complete a self-report assessment about opioid overdose as outlined in **Table 3**. If a participant reports an overdose, research staff will refer her to the clinic staff who will follow up each case as specified in the site clinical SOP. A self-reported overdose resulting in naloxone rescue will be collected as an SAE.

7.3.9 Infant Sedation

The limited data available has revealed low levels of BUP and BUP metabolites in the breastmilk of BUP-maintained women¹¹⁹ and breastfeeding is recommended for stable BUP-maintained women.¹²⁰ However, more data on potential infant exposure through breastfeeding is needed for BUP-maintained women and data on BUP/NX-maintained women⁶⁷ and BUP-XR-maintained women is lacking. While no adverse reactions are expected in breastfed infants in the present study, a theoretically possible and concerning adverse reaction, infant sedation, will be assessed via mother-report as outlined in **Table 3**. The infant sedation assessment will be completed by participants who are feeding their infants with breastmilk and/or formula and will assess for signs of infant sedation (e.g., not waking for feeding, difficulty breathing, etc.). In addition, if an infant sedation assessment in a breastfed infant meets the criteria of an SAE, it will be collected as an SAE, as all infant SAEs occurring in breastfed infants will be collected.

7.4 Covariates

There are a number of variables with the potential to impact mother-infant outcomes and, thus, either mask or exaggerate study medication effects. Randomization will help ensure that the BUP-XR and BUP-SL groups are balanced on these variables, however, they can still be an important source of variance. Analyses will control for these variables, referred to as covariates.

Pregnancy and Addiction Services Assessment (PAASA). Study site will be included as a covariate in the secondary analyses. As noted in **section 6.4.1**, all MOMs sites will use a collaborative care model but will likely differ in the specifics of the care model used (e.g., psychosocial treatment provided etc.), which could impact mother outcomes. A review of the

literature failed to identify an instrument for characterizing models of care for the management of pregnant women with OUD. Hence, an assessment was developed for use in this protocol, the PAASA, which will be used to characterize the treatment provided by the MOMs sites. The PAASA will also be used for the health economic analysis (see **section 10.9**); the PAASA data will likely need to be supplemented with data collected through semi-structured interviews (e.g., can be collected by e-mail correspondence, phone, or in-person interviews) for this purpose. In CTN-0080, a staff member from each site will complete the PAASA at two time-points (i.e., pre-site initiation and near the end of participant data collection).

7.4.1 Covariates for Mother Outcomes

Two covariates will be controlled for in the mother outcomes in addition to study site: 1) the use of other substances at baseline, which can impact both treatment adherence and illicit opioid use and 2) route of illicit opioid use (intravenous vs. not intravenous); the Phase 3 CAM2038 trial found that illicit use outcomes were significantly better for CAM2038, relative to BUP-SL, for participants with intravenous use.⁵⁹

7.4.2 Covariates for Infant Outcomes

The list of potential covariates for infant outcomes is provided in **Table 2**. The mother-related and infant-related covariates will be assessed in the process of collecting other outcome measures (e.g., UDS will capture substance use, including nicotine use, etc.) whereas the delivery hospital-related covariate needs to be obtained from the delivery hospitals; the BORN Survey will be used to obtain these data.

Table 2. Covariates for Infant Outcomes

Mother-related Covariates
Tobacco use ^{81, 121, 122}
UDS positive for: 1) substance of abuse; 2) illicit-opioids only ^{32, 80}
Exposure (yes vs. no) to psychiatric medications (e.g., antidepressants, benzodiazepines, gabapentin, etc.) during pregnancy ^{81, 123, 124}
Infant-related Covariates
EGA at delivery ^{81, 82}
Birthweight ^{81, 82}
Pharmacotherapy received for NAS/NOWS ^{125, 126}
Breastfed while in the hospital ^{127, 128}
NAS/NOWS scoring procedure utilized (e.g., Finnegan, Eat Sleep Console, other) ^{129, 130}
Delivery Hospital-related Covariate
Minimum days of observation for NAS/NOWS for infants exposed to long-acting opioids ¹³¹

BORN Survey. The Better Outcomes Through Research for Newborns (BORN) network of the Academic Pediatric Association created the BORN survey, which assesses hospital characteristics and all aspects of NAS/NOWS management.⁶² The BORN survey was recently used to assess practices for managing NAS/NOWS in BORN-affiliated hospitals; 76 hospitals, located in 34 states completed the BORN survey, with the results revealing significant diversity in approach across hospitals.⁶² The delivery hospital-related covariate in **Table 2** will be assessed by having a staff member from delivery hospitals meeting the criteria outlined in **section 6.4.1** (i.e., written protocol for NAS/NOWS management, etc.) complete the BORN survey at two time-points; staff will be reimbursed for their time. If a participant delivers at a different hospital than originally planned, an attempt will be made to obtain a completed BORN survey for the hospital if one has not been obtained previously.

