10.1.2 Secondary Hypotheses

It is also hypothesized that the BUP-XR, relative to the BUP-SL, group will have better:

1. Mother outcomes during pregnancy including significantly:
 - greater proportion of BUP adherent days during pregnancy
 - greater proportion of drug-negative urine samples
 - less opioid craving as assessed by the opioid craving scale
 - better prenatal care utilization as assessed with the APNCU index
2. Mother outcomes postpartum including significantly:
 - greater proportion of BUP adherent days
 - greater proportion of drug-negative urine samples
 - fewer opioid overdoses
 - less opioid craving as assessed by the opioid craving scale
3. Infant outcomes including significantly:
 - lower proportion of infants requiring opioid medication
 - shorter infant hospital length of stay
 - lower proportion of infants for whom adjunct medications are used to treat NOWS
 - lower proportion of infants with an ICD-10 code indicative of NOWS
 - larger head circumference
 - greater weight and length
 - greater gestational age at delivery
 - greater proportion of infants scoring above the ASQ-3 cut-off

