10.3 Analysis Plan

Each primary and secondary efficacy outcome measure will be analyzed for the intent-to-treat (ITT) population.

The primary outcome will be assessed at a 2.5% significance level for non-inferiority, as recommended by the FDA.¹⁷⁶ If the test of BUP-XR being non-inferior to BUP-SL is statistically significant, then the superiority of the extended-release formulation over the sublingual formulation will be evaluated. There is no need to adjust for this second test if the initial test of non-inferiority is statistically significant. The infant key secondary outcome will be analyzed at the 5% significance level for superiority, and will be interpreted cautiously given the lack of adjustment for multiple testing and will use confidence intervals where possible. The other key secondary outcome (illicit opioid abstinence during postpartum) will be assessed at a 2.5% significance level for non-inferiority.

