Total days of opioid treatment. Total days of infant opioid treatment will be obtained from the medical record. There are extensive covariates to be included in modelling for the infant outcomes (**Table 2**) at the mother-, infant-, and delivery-hospital-level. Explanation for these covariates is provided in **section 7.4**. Since this outcome measure is a count variable and there are covariates requiring adjustment, modelling will utilize Poisson regression. The treatment effect will be measured by the regression coefficient for treatment assignment in the model ($H_0: \beta=0$; $H_1: \beta \neq 0$).

Illicit opioid abstinence during postpartum. The analytic approach will follow the one outlined above for testing the primary outcome.

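### The model for infant opioid-treatment days adjusts for variables that arise after randomization, notably infant pharmacotherapy, so its arm coefficient does not estimate the total effect of assignment

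*Combined protocol and SAP*

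**What the plan says.** Section 7.1.2.1 defines the outcome: "NOWS severity will be assessed by total days of opioid treatment during the hospital stay". Section 10.3 sets the test: "The infant key secondary outcome will be analyzed at the 5% significance level for superiority". Section 10.3.2 chooses the model: "Since this outcome measure is a count variable and there are covariates requiring adjustment, modelling will utilize Poisson regression". The hypothesis test is on the coefficient for treatment assignment.

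Three places bear on the covariates:

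- Section 7.4, general rule: "Analyses will control for these variables, referred to as covariates".
- Section 10.3.2, for this outcome, with a pointer to Table 2: "There are extensive covariates to be included in modelling for the infant outcomes".
- Section 7.4.2, which introduces Table 2 less firmly: "The list of potential covariates for infant outcomes is provided in" Table 2.

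Table 2 lists maternal tobacco use, maternal urine drug screen (UDS) positivity, psychiatric-medication exposure during pregnancy, estimated gestational age (EGA) at delivery, birthweight, "Pharmacotherapy received for NAS/NOWS", in-hospital breastfeeding, the scoring procedure used, and the delivery hospital's minimum observation period. How the pharmacotherapy item is coded is not stated. No unadjusted or baseline-only model for opioid days is named.

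Section 10.1.2 hypothesizes that BUP-XR will lower the share of infants needing opioid medication, raise infant weight, and lead to "greater gestational age at delivery".

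**The concern.** Adjustment for variables fixed before randomization keeps the randomized comparison and usually sharpens it. Adjustment for variables that treatment can change does neither reliably. The coefficient becomes a direct effect with some pathways blocked, and conditioning on a consequence of treatment can open new confounding.

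Pharmacotherapy received is the extreme case, because it decides whether the outcome is zero. Once it is in the model, the arms are compared only among treated infants, and the plan itself expects BUP-XR to change who those infants are.

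Section 7.4 justifies adjustment by saying that randomization helps balance these variables but that they still add variance. That reasoning does not reach variables that arise later. The plan draws the distinction elsewhere: section 7.4.1 takes mothers' other-substance use at baseline.

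At stake is the only superiority test among the three key hypotheses. A null or positive result could not be read as the effect of assigning BUP-XR.

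**Working it through.** **The plan's own figures.** The document gives no power or effect size for infant opioid days. Its only power figures (Table 8) concern the primary outcome. With variance 0.11 (SD 0.332), margin 0.15 and one-sided 2.5%, power = Φ(0.15 / (0.332 × √(4/N)) − 1.96).

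- N = 176: 0.15/0.0500 = 3.00, Φ(1.04) = 85.1%, against 84.9% stated.
- N = 200: 0.15/0.0469 = 3.20, Φ(1.24) = 89.2%, against 89.0% stated.

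These reproduce and are not in question.

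**What adjustment does.** Let p be the share of infants treated with opioids and m the mean days among those treated. Untreated infants contribute 0, so mean days in an arm are p × m, and

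total rate ratio = (p_XR / p_SL) × (m_XR / m_SL).

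A Poisson model with arm alone estimates this product. Add a treated yes/no term and the fitted mean for untreated infants goes to 0 in both arms. They then carry no information about arm, and the coefficient estimates log(m_XR / m_SL). The first factor is lost. Drug type with a level for no drug does the same, because that level is the untreated group.

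**Inputs.** From the document: N = 200, 1:1 (section 10.4.2), and two-sided 5% (sections 10.3 and 10.3.2). The 50% on BUP-SL is section 4.4.2's NAS/NOWS incidence, used here as the treated share, which is an assumption. Also assumed: 15 days among treated BUP-SL infants, the BUP-XR values below, gamma-Poisson spread with shape 3, and robust standard errors. Each scenario has 1,000 simulated trials.

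| BUP-SL to BUP-XR | Total ratio by formula | Arm only: ratio (rejection) | With pharmacotherapy: ratio (rejection) | Log effect kept |
|---|---|---|---|---|
| Share 50% to 30%, 15 days in both | 0.60 × 1.00 = 0.60 | 0.59 (62%) | 1.00 (5%) | about 0 |
| Share 50% to 40%, days 15 to 12 | 0.80 × 0.80 = 0.64 | 0.64 (58%) | 0.80 (43%) | ln 0.80 / ln 0.64 = 50% |
| Share 50% to 30%, days 15 to 10 | 0.60 × 0.67 = 0.40 | 0.39 (99%) | 0.66 (84%) | ln 0.66 / ln 0.40 = 45% |
| Share 50% in both, days 15 to 10 | 1.00 × 0.67 = 0.67 | 0.67 (57%) | 0.67 (91%) | about all |

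The adjusted column was fitted on treated infants, which the algebra shows is equivalent. A fit to 20,000 infants with the yes/no term in the full data, for the first scenario, also gave 1.00. Adding drug type among treated infants changed no ratio.

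**The other Table 2 items, side by side with the rest of the plan.**

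- EGA at delivery and birthweight are covariates in Table 2 and hypothesized BUP-XR effects in section 10.1.2.
- Section 4.4.2 states that later gestation goes with more severe NOWS. If BUP-XR lengthens gestation, that path raises opioid days. Holding EGA at delivery fixed removes the path and could make BUP-XR look better than its total effect.
- In-hospital breastfeeding occurs after birth.
- Maternal UDS and tobacco use have no stated time window. Urines taken after randomization are the data behind the primary outcome (section 7.1.1); a screening urine is also taken (Table 3).
- Psychiatric-medication exposure covers all of pregnancy, while randomization falls at 6 to 30 weeks, so part of it precedes randomization and part may not.

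**The case against.** Several points on the other side have force.

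- **A reader might infer that any real NOWS effect is adjusted away, or that the bias always runs toward no effect.** The documents do not support either. An effect on duration alone survives with higher power (57% to 91%), mixed effects keep about half on the log scale, and adjusting for EGA at delivery could favor BUP-XR. What survives is still a comparison within a subgroup selected after randomization.
- **The covariate list is not settled.** Section 7.4.2 presents it as candidates, and section 4.4.2 speaks of control where necessary. This stands as a conflict in the text, but sections 7.4 and 10.3.2 are firm. The standalone SAP is mentioned only for the power simulation (section 10.4.2).
- **The item may mean drug type.** The titles of the two cited references point that way. Drug type is still undefined for untreated infants, so they are either dropped or placed at a level that fixes their days at zero.
- **Table 2 serves all infant outcomes.** For others, such as the ASQ-3, pharmacotherapy does not determine the outcome. A reader might also infer that the test of the share of infants needing opioid medication is spoiled. Section 10.3.3 allows a chi-square test there and lists no covariates, so it is affected only if Table 2 is applied to it.
- **Not every zero is settled by the covariate.** Section 10.3.5 imputes the greatest observed days when there is no live birth or no record. The argument concerns infants with records; how imputed cases would enter a covariate-adjusted model is not stated.
- **The result is key secondary and will be read cautiously.** Section 10.3 ties that caution to multiplicity, which does not address what the coefficient estimates.

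**Conclusion.** The point holds. As written, the Poisson model for infant opioid days conditions on post-randomization variables, and its arm coefficient does not estimate the total effect of assignment. Adjusting for pharmacotherapy received removes the treated-or-not component in full and leaves the duration component, under yes/no coding or drug type with a level for none. This follows from the definition of the outcome and does not depend on the simulation.

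The sizes do depend on assumptions: the 50% treated share, the 15 days, the effect sizes and the spread are not plan values for this outcome, and the rejection rates also rest on robust standard errors. The pattern is the finding. For EGA at delivery, birthweight, breastfeeding, and maternal items when measured after randomization, the size and direction of bias cannot be stated from the documents.

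The primary analysis uses only arm and the three randomization factors (section 10.3.2) and is not affected.

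**What to change.** 1. In section 10.3.2, make the main opioid-days model arm plus the randomization factors (site, EGA stratum, BUP-SL status at randomization).
2. Limit any further adjusters to variables fixed before randomization and list them. Examples are baseline tobacco and other-substance use, psychiatric medication before randomization, and the planned delivery hospital's practice from the BORN survey.
3. Remove pharmacotherapy received from the covariates for this outcome.
4. Move EGA at delivery, birthweight, breastfeeding and maternal measures taken after randomization to labelled mediation or sensitivity analyses; section 10.8 is a natural place.
5. Reconcile sections 7.4.2 and 10.3.2 on whether the list is optional, and state which infant outcomes it covers.

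The change is to wording only: baseline urines, substance-use history, medication history and the BORN survey are already collected. The downside is that somewhat less residual variance is explained. The covariate set should be fixed before outcome data are seen.
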